- Cohort 2: Dose Level 2: Amph-CpG-7909 0.5 mg with Amph-Peptides
- Cohort 3: Dose Level 3: Amph-CpG-7909 2.5 mg with Amph-Peptides

Cohorts will consist of 3 to 6 subjects (the number will depend on whether DLTs are observed). In order to ensure an adequate number of evaluable subjects, up to 6 subjects may be enrolled per cohort even in the absence of a DLT. Once the RP2D is determined, the cohort evaluating the Phase 2 dose will be expanded as needed so that there is safety experience with at least 6 subjects at this dose level.

Dose escalation from one cohort to the next will be determined by the Safety Monitoring Committee (SMC), and will be based on treatment-emergent AEs, clinical laboratory data, physical examination (PE) findings including vital signs, after all subjects within a cohort have completed 28 days. At each SMC meeting, longer follow-up will be available on all but the final subject in each cohort. The SMC will review all available long-term safety information from prior cohorts (if any), so that the SMC will consider the totality of the safety information in their recommendation.

In any cohort, if none of the subjects experience a DLT during the first 28 days following first administration of ELI-002, dose escalation will occur, and 3 subjects will be enrolled in the cohort at the next dose level. However, if 1 of the 3 or 4 initial subjects in a cohort experiences a DLT, then 3 (or 2, if 4 were originally enrolled) additional subjects will be enrolled at the same dose level. If 2 or more of 3 subjects within a cohort experience a DLT, then this dose will be considered the toxic

dose. If only 1 of 6 subjects within a cohort experiences a DLT during the first 28 days of treatment, then the next cohort may begin enrollment. If 2 or more of 6 subjects within a cohort experience a DLT during the first 28 days, then this dose will be considered the toxic dose. The trial may proceed at a lower dose, at a less frequent schedule, or omitting the Amph-CpG-7909 adjuvant while continuing to administer the Amph-Peptides, based on emerging toxicity or pharmacodynamic data until the MTD is determined.

A trial memo will be sent to all sites following each SMC cohort review meeting summarizing the decision; if additional cohorts are to be enrolled, the dose level and schedule will be provided.

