### **6.6. Safety Criteria for Temporarily or Permanently Stopping the Trial**

The sponsor medical monitor will be continuously monitoring the safety of subjects. In addition, the cumulative safety will be reviewed by the SMC at the following key time points:

- After the last subject in each cohort completes the DLT observation period
- Ad hoc as necessary

The trial may be temporarily or permanently stopped by the sponsor, if any subject death occurs attributed to administration of ELI-002 (ie, if there is Grade 5 toxicity that is definitely, probably, or possibly attributed to trial treatment).

Any potential re-initiation of the trial will be discussed by the Sponsor, with the support of the SMC and in consultation with the FDA, if necessary.

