## 10. TIMING OF TRIAL PROCEDURES

Home Health Visits: Based on assessment of risk, and to ensure subject safety and minimize risks to trial integrity, off-site study visits can be performed in the event a study participant cannot attend an on-site visit during the COVID-19 crisis [[Food and Drug Guidance, 2020](#)]. The procedures that cannot be performed during a home health visit include:

- CT/MRI scans
- First ELI-002 dose administration (Visit 3, Day 57); this must occur on-site as per Section [10.2](#).
- Leukapheresis (Visit 2, Visit 9)

The informed consent form will describe the availability of home health visits if applicable at the clinical site.

The subject will be invited to continue future study visits on-site per protocol, as soon as local and federal Covid-19 regulations allow.

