## 10.2. Immunization Period

During the Immunization Period, subjects will receive 4 weekly SC injections (Weeks 1 to 4) followed by 2 injections at Week 6 and Week 8 (Table 12). If the subject has fever  $\geq 38.0^{\circ}\text{C}$  and/or elevated IL-6  $\geq 500$  pg/mL, proceed with the visit but omit study treatment administration; if fever abates and cytokines diminish to  $< 500$  pg/mL, the subject may proceed with the next scheduled dose after approval from the medical monitor). In addition, if a subject exhibits IFN $\gamma$   $\geq 1000$  pg/mL, the Elicio medical monitor should be contacted for consultation.

All laboratory samples should be taken prior to dosing on any study visit that has dosing.

At **Visit 3 (Baseline, Day 57) prior to trial drug administration**, the following visit procedures will include:

- Administer the EORTC QLQ-C30 and the tumor type-specific PRO (see Section 11.3).
- Record any change in medical history since the previous visit. Subjects must have recovered from surgery without any ongoing medical/surgical issues.
- Record any change in cancer history since the previous visit.
- Perform a physical examination which will be based on institution standard of care (see Section 12.1.3). In addition, a neurological examination for baseline assessment of ICANS/ICE will be performed.
- Record vital signs (blood pressure, pulse rate, body temperature, and respiratory rate).
- Record weight.
- Perform a 12-lead ECG (to be reviewed by a cardiologist or clinical investigator according to institutional guidelines and practice).
- Confirm ECOG Scale of Performance Status is 0 or 1.
- Record any change in concomitant medications since the previous visit.
- Collect a blood sample for clinical laboratory assessments, including the cytokine panel (local laboratory; see Section 11.1 and Section 12.1.6). Note: cytokine testing should be performed within 7 days prior to dosing.
- Collect a blood sample for ctDNA (to be performed at a central laboratory).
- Collect a blood sample for high resolution HLA typing (central laboratory).
- Record any pre-treatment SAEs that have occurred since the previous visit.

**Dose 1:** The first dose must be administered at the clinical site. Subjects must be observed by study staff for at least 1-hour postdose for observation and must stay within an hour of the clinic for  $\geq 24$  hours in order to monitor for potential AEs such as CRS.

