- Record vital signs (blood pressure, pulse rate, body temperature, and respiratory rate). Measurements will be obtained after 3 minutes in the sitting position. No other measurements or procedures were performed during this 3-minute period.
- Record weight.
- Confirm ECOG Scale of Performance Status.
- Record any change in concomitant medications since the previous visit.
- All laboratory samples should be taken prior to dosing on any study visit that has dosing.
  - Collect a blood sample for clinical laboratory assessments, including the cytokine panel (local laboratory; see Section 11.1 and Section 12.1.6). Note: cytokine testing should be performed and reviewed within 7 days prior to dosing.
  - Collect a whole blood sample for immunogenicity testing (central laboratory).
- Record any AEs since last visit. Check for signs of toxicity, including fever and laboratory evidence of elevated cytokines. Hold the ELI-002 dose if Grade  $\geq 2$  CRS is present, or if elevated cytokine IL-6 is present. If elevated IFN $\gamma$  is present, the Elicio medical monitor should be contacted for consultation (Section 6.8.1).
- **Dose 3:** Trial drug administration and subjects must be observed for safety for at least 1-hour postdose.
- Subjects will be provided with the reactogenicity diary to complete for 7-days following the dose. Subjects will be instructed how to complete the diary and to return the completed form at their next visit.

At **Visit 6 (Day 78)**, the following visit procedures will include:

- Administer the EORTC QLQ-C30 and the tumor type-specific PRO (see Section 11.3).
- Perform a physical examination, which will be based on institution standard of care (see Section 12.1.3).
- Record vital signs (blood pressure, pulse rate, body temperature, and respiratory rate). Measurements will be obtained after 3 minutes in the sitting position. No other measurements or procedures were performed during this 3-minute period.
- Record weight.
- Confirm ECOG Scale of Performance Status.
- Record any change in concomitant medications since the previous visit.
- All laboratory samples should be taken prior to dosing on any study visit that has dosing.
  - Collect a blood sample for clinical laboratory assessments, including the cytokine panel (local laboratory; see Section 11.1 and Section 12.1.6). Note: cytokine testing should be performed and reviewed within 7 days prior to dosing.

- Collect a blood sample for ctDNA.

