- Record any AEs since last visit. Check for signs of toxicity, including fever and laboratory evidence of elevated cytokines. Hold the ELI-002 dose if Grade  $\geq 2$  CRS is present, or if elevated cytokine IL-6 is present. If elevated IFN $\gamma$  is present, the Elicio medical monitor should be contacted for consultation ([Section 6.8.1](#)).
- **Dose 4:** Trial drug administration and subjects must be observed for safety for at least 1-hour postdose.
- Subjects will be provided with the reactogenicity diary to complete for 7-days following the dose. Subjects will be instructed how to complete the diary and to return the completed form at their next visit.

At **Visit 7 (Day 92)**, the following visit procedures will include:

- Administer the EORTC QLQ-C30 and the tumor type-specific PRO (see [Section 11.3](#)).
- Perform a physical examination, which will be based on institution standard of care (see [Section 12.1.3](#)).
- Record vital signs (blood pressure, pulse rate, body temperature, and respiratory rate). Measurements will be obtained after 3 minutes in the sitting position. No other measurements or procedures were performed during this 3-minute period.
- Record weight.
- Confirm ECOG Scale of Performance Status.
- Record any change in concomitant medications since the previous visit.
- All laboratory samples should be taken prior to dosing on any study visit that has dosing.
  - Collect a blood sample for clinical laboratory assessments, including the cytokine panel (local laboratory; see [Section 11.1](#) and [Section 12.1.6](#)). Note: cytokine testing should be performed and reviewed within 7 days prior to dosing.
  - Collect a whole blood sample for immunogenicity testing (central laboratory).
- Record any AEs since last visit. Check for signs of toxicity, including fever and laboratory evidence of elevated cytokines. Hold the ELI-002 dose if Grade  $\geq 2$  CRS is present, or if elevated cytokine IL-6 is present. If elevated IFN $\gamma$  is present, the Elicio medical monitor should be contacted for consultation ([Section 6.8.1](#)).
- **Dose 5:** Trial drug administration and subjects must be observed for safety for at least 1-hour post dose.
- Subjects will be provided with the reactogenicity diary to complete for 7-days following the dose. Subjects will be instructed how to complete the diary and to return the completed form at their next visit.

At **Visit 8 (Day 106)**, the following visit procedures will include:

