**Table 8: Derived variables**

Variables	Formula
Demographic and Baseline characteristics	
Body mass index (BMI) (kg/m  )	weight (kg)/[height (m)] 
Derivation of Duration	
Study day at any visit	Date of interest – date of first dose of study treatment. One day is added if this difference is ≥ 0
Duration of study (Days)	(Date of study completion/discontinuation (for discontinued subjects) – date of first dose) + 1
Duration of Exposure to the study treatment ( weeks )	Is [last date of booster dose – first date of immunization dose] + 1] / 7. IF treatment discontinuation, then last date of booster dose = last dose date prior to or at the date of treatment discontinuation.
Treatment Exposure and Compliance	
Cumulative Planned volume (mL)	Total planned volume for each dose* Planned number of doses for the duration of exposure
Cumulative actual volume administered (mL)	Total actual volume administered from exposure CRF page (Cumulative value of 'Actual volume administered' from Study Drug Administration)
Expected Dose	Calculated as the expected number of vaccinations multiplied by assigned dose in mg
Compliance (%)	(Cumulative actual volume administered /Cumulative planned volume)*100
Dose intensity (DI) for ELI-002 Amph-Peptides 2P	Amount of actual cumulative dose of ELI-002 Amph-Peptides 2P (mg) divided by expected dose given for a full 10 course of vaccinations.
Dose intensity (DI) for ELI-002 Amph-CpG-7909	Amount of actual cumulative dose of ELI-002 Amph-CpG-7909 (mg) divided by expected dose given for a full 10 course of vaccinations.
Relative dose intensity	Cumulative dose received divided by expected dose and multiplied by 100
Baseline Derivations	
Baseline value	Unless otherwise specified, the baseline value is defined as the last non-missing observation prior to administration of the first dose of study treatment. For most assessments, this would be the Visit 3 value. If Visit 3 is missing, the Visit 2 value will be used.
Change from baseline	Post baseline value – Baseline value
Fold change from baseline	(Post baseline value – Baseline value)/Baseline value
Biomarker Reduction/Clearance	
Note: All reporting will select the biomarker (ctDNA, CEA, or CA-19) which contains the best (i.e., largest decrease post-baseline) result per subject. If there is no decrease for a given subject, then “best” is the smallest increase.	

**Final Analysis  
Statistical Analysis Plan (SAP)**

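### The 28-day escalation review can precede all scheduled laboratory, examination and AE-review data after Dose 4 in the last-dosed subjects

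*Protocol*

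**What the plan says.** **Visit calendar.** Protocol Section 10 reads "First ELI-002 dose administration (Visit 3, Day 57", so Day 57 is the day of Dose 1. Section 10.2 sets out "4 weekly SC injections (Weeks 1 to 4) followed by 2 injections at Week 6 and Week 8". In Table 12, Dose 4 is given at Visit 6 (Day 78 ±3) and Dose 5 at Visit 7 (Day 92 ±3), with no visit between them.

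**What Visit 6 collects.** Section 10.2 states: "All laboratory samples should be taken prior to dosing on any study visit that has dosing". The Visit 6 examination, vital signs and AE check are also listed ahead of the dose; vital signs after dosing are specified only for Dose 1. The Dose 4 diary is kept at home for 7 days. On its return the plan says: "Subjects will be instructed how to complete the diary and to return the completed form at their next visit". That visit is Visit 7.

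**When the SMC decides, and on what.** The DLT window is 28 days (Protocol Section 6.7.3), counted from first dose in SAP Section 8.1. Escalation rests on treatment-emergent AEs and on "clinical laboratory data, physical examination (PE) findings including vital signs, after all subjects within a cohort have completed 28 days" (Synopsis, repeated in Sections 4.6.4, 6.1 and 6.1.1 and in SAP Section 8.1). Section 6.6 sets the cumulative safety review "After the last subject in each cohort completes the DLT observation period". The Synopsis and Section 6.1 add that "longer follow-up will be available on all but the final subject in each cohort". The 1-week stagger applies between the first subject of a cohort and those who follow, not among the later ones.

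**The concern.** The escalation rule names data that the schedule does not collect in the last part of the DLT window. Dose 4 always falls inside the window. The next laboratory panel, examination, set of vital signs, AE review and diary return always fall outside it. A subject who has just completed 28 days has none of these after the fourth dose, when cumulative exposure in the window is at its highest.

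The interim decision to open the next cohort is what this affects. The trial is first-in-human, the three planned adjuvant levels rise in 5-fold steps (0.1, 0.5, 2.5 mg), and Section 4.4.1.2 attributes the mouse toxicity mainly to the adjuvant. The assurance about longer follow-up also falls short. It concedes the point for the final subject, and the stagger does not secure it for the others, because subjects 2 and 3 may be dosed on the same day.

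**Working it through.** **Inputs.** Visit days and ±3-day windows from Protocol Table 12; 28-day DLT window from Section 6.7.3 and SAP Section 8.1; study-day rule from SAP Table 8 (date minus first-dose date; "One day is added if this difference is ≥ 0").

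**Check against the plan's own figures.** Weeks from first dose = (visit day − 57)/7. Visit 6: (78 − 57)/7 = 3. Visit 7: (92 − 57)/7 = 5. Both match Table 1-1 of the SAP's immunogenicity and ctDNA addendum.

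**Nominal position.**
- Dose 4: 78 − 57 = 21 days after Dose 1 (study day 22).
- End of 28 days: Day 57 + 28 = 85.
- Visit 7: 92 − 57 = 35 days after Dose 1 (study day 36).
- The 28-day point is thus 7 days after Dose 4 and 7 days before Visit 7.

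**All permitted windows.**
- Dose 4, earliest 75 − 60 = 15 days after Dose 1, latest 81 − 54 = 27. It is always inside the window, with 1 to 13 days of the window left after it.
- Visit 7, earliest 89 − 60 = 29 days after Dose 1, latest 95 − 54 = 41. It is never inside the window.

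No allowed combination closes the gap. Counting the dosing day as day 1 moves the 28-day point one day earlier and changes neither statement.

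**Stagger.** If a later subject is dosed 7 days after the first, the first is at 28 + 7 = 35 days when the later one reaches 28. That is the nominal day of Visit 7, so even the first subject's Visit 7 data may only just be due.

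**Illustration of size.** The documents give no DLT rate or timing. Assume a true 28-day DLT probability of 1/3 and equal risk for each of four doses, so that 1/4 of DLTs follow Dose 4. An affected subject then appears DLT-free with probability 2/3 + (1/3)(1/4)u, where u is the share of post-Dose 4 DLTs not known at the meeting.

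| | u = 0 | u = 1 (none surface) | u = 0.5 (half surface) |
|---|---|---|---|
| Affected subject appears DLT-free | 0.667 | 0.750 | 0.708 |
| P(0 of 3 seen), one subject affected | 0.296 | (2/3)² × 0.750 = 0.333 | (2/3)² × 0.708 = 0.315 |
| P(0 of 3 seen), two subjects affected | 0.296 | (2/3) × 0.750² = 0.375 | (2/3) × 0.708² = 0.334 |

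The u = 0 column is (2/3)³ = 0.296. If instead 40% of DLTs follow Dose 4 and none surface, the figures are (2/3)² × 0.80 = 0.356 and (2/3) × 0.80² = 0.427.

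**The case against.** A reader might infer that the MTD/RP2D endpoint itself loses events after Dose 4. The documents do not support that. Visit 7 records AEs since the previous visit, Section 12.5 requires an onset date for each, and the MTD is defined on the cohort's DLT incidence. In-window events can therefore enter that count about a week later. The RP2D also requires at least 6 subjects at the dose and, under Section 4.6.5, weighs toxicities beyond the DLT window. The SMC can also meet ad hoc (Section 6.6). This objection stands and confines the point to the interim decision.

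A reader might also infer that nothing is known after Dose 4. That too goes beyond the documents. There is a 1-hour post-dose observation with reactogenicity capture, continuous medical-monitor review, SAE reporting within 1 business day, CRS and ICANS on SAE timelines, advice to seek immediate care for CRS symptoms, and provision for unscheduled re-tests. Cytokines for Dose 5 may be drawn up to 7 days early, nominally at 28 days (22 to 34 with windows). Many Grade 3 events would also qualify as SAEs. These routes reduce the gap. None is a required post-Dose 4 laboratory panel, examination or diary return.

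Two narrower objections also hold in part. Section 12.2.1.3 says routine injection-site reactions, rash and pruritis are not DLTs, so the diary adds little to the DLT count, although systemic symptoms could matter. Asymptomatic laboratory abnormalities are excluded under DLT criterion (a), so a DLT found only by laboratory test would come mainly through the criterion for major-organ toxicity lasting more than 72 hours.

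Finally, 28 days is the earliest review point, not a fixed meeting date. Section 6.1.1 refers to an SMC Charter, which was not available for this review and may set the data cut. The protocol and SAP neither require nor forbid waiting for Visit 7.

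**Conclusion.** The mismatch is real and follows from the documents' own calendar: no permitted visit window places Visit 7 within 28 days of Dose 1. As written, escalation can be decided with no scheduled laboratory, examination, vital-sign, AE-review or diary data after Dose 4 for one or more of the last-dosed subjects. The risk is to that decision and to the next cohort, not to the final MTD/RP2D determination.

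The size is uncertain. Under the equal-risk assumption, the rise in P(0 of 3 seen) from 0.296 to 0.333 or 0.375 is an upper bound, because it supposes that no post-Dose 4 DLT surfaces by another route. If half surface, the figures are 0.315 and 0.334. The surfacing rate is an assumption either way. The point merits correction because the change is cheap; it does not show that any escalation was unsafe.

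**What to change.** Reconcile the 28-day review point with the visit calendar in the Protocol Synopsis, Sections 4.6.4, 6.1, 6.1.1 and 6.6, SAP Section 8.1 and the SMC Charter, so that the data the SMC is said to review exist when it decides. The Visit 7 pre-dose AE review, laboratory results, examination and vital signs, with the returned Dose 4 diary, are already scheduled and would supply them. The sentence on longer follow-up for all but the final subject should be aligned with what the stagger secures. Doses, the DLT definition and the 28-day window are unchanged.

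The cost is wording, plus a wait per escalation step of nominally 35 − 28 = 7 days, ranging from 29 − 28 = 1 to 41 − 28 = 13. No visit or procedure is added.

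The Synopsis gives 2Q2023 for last enrolment and the SAP cites a protocol version dated 07 Aug 2023, so escalation may already be complete. In that case, the study report should state which post-Dose 4 data each SMC decision held for each subject.

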### 10.3. No Dosing 3-Month Period

After the Immunization Period, subjects will be observed during a No Dosing 3-Month Period ([Table 13](#)).

At **Visit 9 (Day 120)**, the following visit procedures will include:

- Administer the EORTC QLQ-C30 and the tumor type-specific PRO (see [Section 11.3](#)).
- Perform a physical examination, which will be based on institution standard of care (see [Section 12.1.3](#)).
- Record vital signs (blood pressure, pulse rate, body temperature, and respiratory rate). Measurements will be obtained after 3 minutes in the sitting position. No other measurements or procedures were performed during this 3-minute period.

- Record weight.
- Record any change in concomitant medications since the previous visit.
- Collect a blood sample for clinical laboratory assessments (local laboratory; see [Section 12.1.6](#)).
- Collect leukapheresis for immunogenicity assessments (central laboratory). This procedure may be performed -7 days to +3 days from Visit 9.
- Record any AEs since last visit.

At **Visit 10 (Day 148)** and **Visit 11 (Day 176)**, the following visit procedures will include:

- Administer the EORTC QLQ-C30 and the tumor type-specific PRO (see [Section 11.3](#)).
- Perform a physical examination, which will be based on institution standard of care (see [Section 12.1.3](#)).
- Record vital signs (blood pressure, pulse rate, body temperature, and respiratory rate). Measurements will be obtained after 3 minutes in the sitting position. No other measurements or procedures were performed during this 3-minute period.
- Record weight.
- Record any change in concomitant medications since the previous visit.
- At **Visit 10 (Day 148 [±14 days])** only perform a CT with contrast. For subjects with IV contrast allergy/intolerance, MRI may be performed. The same modality as the screening imaging assessment should be used throughout the trial.
- Collect a blood sample for clinical laboratory assessments (local laboratory; see [Section 12.1.6](#)).
  - At Visit 11 (Day 176) only – collect a blood sample for the cytokine panel (local laboratory; see [Section 11.1](#)). Note: cytokine testing should be performed and reviewed within 7 days prior to dosing.
- At **Visit 10 (Day 148 [±14 days])** only collect a serum sample for CA-125/CA 19-9/CEA for appropriate tumor type (local laboratory).
- At **Visit 11 (Day 176)** only collect a blood sample for ctDNA (to be performed at a central laboratory):
- At **Visit 11 (Day 176)** collect a whole blood sample for immunogenicity testing (central laboratory)
- Record any AEs since last visit.

